## 2.0 OBJECTIVES

### 2.1 Primary Objectives

To conduct a single-arm study to assess feasibility and acceptability of two smartphone apps and a wearable accelerometer in 30 patients with gynecologic cancers receiving chemotherapy.

- Feasibility will be defined as: 1) ≥50% approach to enroll rate, and 2) ≥50% 3-month adherence rates to both smartphone apps and the wearable accelerometer.
- Acceptability will be defined as: ≥60% of study participants would recommend the intervention to other patients; and <30% of patients rate the study as burdensome or wish they had not participated.

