### **5.23 Debriefing Interviews**

Debriefing Interviews will be conducted with a purposively sampled subset of participants, approximately 15 across all sites. The purpose of these interviews is to obtain information about the acceptability of the interventions and recommendations for modifications to improve any aspect of recruitment, enrollment, education, timing of study assessments, the graphical display of information, and the smartphone apps. The interview guide can be found in Appendix 20. In accordance with qualitative interviewing procedures, additional themes and topics that arise over the course of the study may be explored further in the debriefing interview, in addition to the list of questions in the interview guide. Study staff will aim to administer debriefing interviews to the first few patients enrolled at each site and an additional purposively sampled subset of patients; debriefing interviews will be conducted for approximately 15 patients total. Study staff will also solicit debriefing feedback from clinicians who are serving as co-investigators on the study and site research staff who are managing the clinician dashboard. If site policy permits, participating co-investigators and site staff will receive gift cards in appreciation of the time they have dedicated to study debriefing. The feedback provided by co-investigators and site staff will be used to further refine integration of the study into clinical workflow and improve the effectiveness of the study.

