#### Debriefing Interview:

- Study staff will aim to conduct debriefing interviews with the first few participants enrolled at each site and a purposively sample a subset of patients who enroll later (up to 15 total).
- Debriefing interviews will be administered by study staff following participants' completion of the final post-baseline survey.
- Study staff will discuss the debriefing interviews to identify opportunities for protocol improvement.

Health/Treatment Chart Abstraction:

- Study staff will review participants' medical charts to complete the Health/Tx Information form for the time-points of participants' baseline and post-baseline visits.

Health Care Utilization Chart Abstraction:

- Study staff will review participants' medical charts to complete the Health Care Utilization form after participants' post-baseline visit.
- Patients will complete the Medical Care Resource Form to capture all health care utilization during the study, including care outside of affiliated sites that may not be captured in site medical records.

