## **6.2. Sample Size**

The primary objective of this study is to assess the feasibility and acceptability rates of the SMART intervention. A convenience sample of 30 patients will be enrolled to the study, with expected accrual of approximately 15 patients each at a maximum of 2 community oncology sites.

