## **6.3 Analysis Plan**

Statistical analysis will be descriptive in nature and will assess feasibility, acceptability, and perceived efficacy, as well as estimate outcomes parameters.

**Feasibility:** Feasibility will be defined as ≥50% approach-to-enrollment rate among eligible participants, and 2) ≥50% 3-month adherence rates to the smartphone app and wearable accelerometer (based upon attrition rates from prior trials of PROs). Patients who complete daily surveys ≥4 days per week over the three-month study period will be considered as adherent to the smartphone app. Patients who wear the wearable accelerometer ≥4 days per week over the three-month study period will be considered as adherent to the wearable accelerometer.

**Acceptability:** Acceptability will be defined as ≥60% of participants “agree” or “strongly agree” that they “would recommend the SMART Study to other patients with cancer receiving chemotherapy;” and <30% of participants answering agree or strongly agree to either question: 1) “Participating in this study placed a substantial burden on me” and 2) “I wish I had not agreed to participate in this study.”

**Perceived efficacy:** Perceived efficacy will be measured by qualitative analysis. We will conduct debriefing interviews with approximately 30 participants and their clinicians (evenly distributed among the community oncology sites) to obtain information about the acceptability of the intervention and recommendations for any modifications to improve any aspects of recruitment, enrollment, education, the timing of study assessments, graphical display of information, and the app that could be improved.

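### SMART's primary acceptability criteria have no denominator and no rule for patients who leave before day 90, so a burdened patient who leaves never counts as burdened

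*Combined protocol and SAP*

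**What the plan says.** Acceptability is one of SMART's two primary endpoints (6.1). The objectives (2.1) require that "≥60% of study participants would recommend the intervention to other patients" and that "<30% of patients rate the study as burdensome or wish they had not participated". The analysis plan (6.3) restates the first part as "Acceptability will be defined as ≥60% of participants" who agree or strongly agree that they would recommend the study, and the second as "<30% of participants answering agree or strongly agree to either question". Both parts must hold. Participants, study participants and patients are used interchangeably, and none is defined.

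On size, 6.2 says only that "A convenience sample of 30 patients will be enrolled to the study". SMART has no missing-data section. Section 5.1 says missing data will be assessed but gives no rule. The only handling rule in the combined document is HOPE 6.5, which covers the EQ-5D.

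On timing, SMART does not name the instrument that carries the three items. They do not appear in Table 1, Table 2 or the list of app surveys in 5.5.1. The single post-baseline interview is at about three months. Debriefing comes later still: "Debriefing interviews will be administered by study staff following participants' completion of the final post-baseline survey".

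**The concern.** All three items look back on the experience of taking part, and no exit assessment is described. The patients most likely to be missing at three months include those who found the daily surveys too much. The protocol recognises this link. SMART 5.31 says that interventions demanding much of patients tend to lose more of them, and that illness may interfere with reporting. Section 5.53 gives limiting attrition as one reason for the gift card. The adherence bar in 6.3 is "based upon attrition rates from prior trials of PROs".

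Burden is therefore measured at a point that burdened patients may not reach, and nothing says how their absence is scored. At stake is whether a primary endpoint is declared met. That answer could depend on a denominator chosen after the data are in.

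**Working it through.** **1. When are the items asked?** The SMART text does not say outright, so the passages have to be read together.
- Table 2 and 5.5.1 place the only post-baseline interview at about day 90.
- Debriefing follows the final survey. Its aim is stated in 5.23: "The purpose of these interviews is to obtain information about the acceptability of the interventions". It reaches about 15 patients according to 5.23 and 5.5.1, but about 30 according to 6.3.
- HOPE 6.4 (first phase) asks the same burden and regret items once the study is complete.

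Asking at about day 90 only is a strong inference, not a stated fact.

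**2. Is there a planned figure to reproduce?** No. The sample of 30 (about 15 at each of at most two sites, 2 × 15 = 30) has no power, precision or dropout calculation behind it.

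**3. What does a pass require?** Let N = 30 enrolled and n = number answering at day 90. The values of n are assumptions.
- Answerers as denominator: recommending r must satisfy r/n ≥ 0.60, and burdened b must satisfy b/n < 0.30.
- All enrolled as denominator, with silence counted as no agree answer: r/30 ≥ 0.60 gives r ≥ 18, and b/30 < 0.30 gives b ≤ 8.

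| n answering | Answerers: least r (as % of 30) | Answerers: most b (as % of n) | All 30: share of n that must recommend | All 30: share of n that may be burdened |
|---|---|---|---|---|
| 30 | 18 (60.0%) | 8 (26.7%) | 18/30 = 60% | 8/30 = 26.7% |
| 24 | 15 (50.0%) | 7 (29.2%) | 18/24 = 75% | 8/24 = 33.3% |
| 20 | 12 (40.0%) | 5 (25.0%) | 18/20 = 90% | 8/20 = 40.0% |
| 18 | 11 (36.7%) | 5 (27.8%) | 18/18 = 100% | 8/18 = 44.4% |
| 17 | 11 (36.7%) | 5 (29.4%) | impossible | 8/17 = 47.1% |
| 15 | 9 (30.0%) | 4 (26.7%) | impossible | 8/15 = 53.3% |

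**4. Can dropout turn a fail into a pass?** Suppose that among all 30, 15 would recommend (50%, fail) and 12 are burdened (40%, fail). Five patients who are burdened and would not recommend leave before day 90.
- Answerers: 15/25 = 60.0% (pass) and (12 − 5)/25 = 7/25 = 28.0% (pass). Acceptability is declared.
- All enrolled: 15/30 = 50.0% (fail) and 7/30 = 23.3% (pass). Acceptability is not declared, but the burden criterion has still flipped.

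**5. Is it attrition as such, or who leaves?** If loss is random, n answerers are a binomial sample. With a true recommend rate of 50%, the chance of reaching 60% is 0.181, 0.154, 0.252 and 0.304 at n = 30, 24, 20 and 15. These values move unevenly because of rounding. The systematic bias comes from loss related to dissatisfaction.

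**The case against.** A reader might infer that early leavers cannot count against acceptability at all, so that attrition by itself delivers a pass. The documents do not support that. If participants means everyone enrolled, each leaver counts against the recommend criterion. Both criteria must hold, so 13 or more leavers (17/30 = 57% at best) make a pass impossible. Under the answerers reading, losing satisfied patients would also push both rates the wrong way.

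A reader might also take the 50% adherence bar to mean that up to half the patients may be missing at day 90. That does not follow. Adherence means surveys or wear on at least four days a week, and a patient who stops using the app can still answer the survey. Staff also try to reach patients whose data stop (5.52d).

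Three further points are fair. SMART is a descriptive pilot without formal testing (5.1). Attrition would also be expected to show in the feasibility endpoint. The item lists are in appendices that are not part of the text, so absence from Table 1 proves little, and the items may well sit in the day-90 survey.

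These points narrow the concern but do not remove it. The thresholds still decide what is declared. Feasibility passes with up to half non-adherent and does not show who was burdened. Placing the items in the day-90 survey would still leave early leavers unasked.

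**Conclusion.** The concern holds in a bounded form. The denominator and the handling of early leavers are undefined for a primary endpoint. Under either reading, a burdened patient who leaves is never counted as burdened, so that criterion is biased towards a pass when burden drives dropout. With answerers as denominator, five dissatisfied leavers out of 30 are enough to turn two failing criteria into two passing ones. With all enrolled as denominator, only the burden criterion is eased, and the recommend criterion becomes stricter.

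This rests on two assumptions: that the items are asked only at about day 90, and that leaving is related to dissatisfaction. The numbers of leavers are illustrations, because the documents give no dropout rate for SMART.

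**What to change.** In 5.5.1 and Table 1, state that the three items are in the day-90 survey for all participants, and ask the same items by phone when a patient withdraws or stops early.

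In 6.3, use one pre-specified denominator for both criteria: all enrolled, with deaths before day 90 reported separately. Report the number missing. Give the responder rate beside a worst-case bound in which non-responders count as not recommending and as burdened. Call the intervention acceptable without qualification only if the conclusion holds under both.

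The cost is three questions at exit, a short call, some plan text, and possibly a less favourable or more qualified statement. The bound is severe: nine non-responders alone give 9/30 = 30% and fail the burden criterion, and in this population silence may reflect illness rather than study burden. It should therefore be a bound and not the only scoring rule.

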## 5.2 Selection of Instruments

### 5.21 Interviews and Surveys

The following measures will be used in the study interviews and surveys, including the *Participant Baseline Interview* (Appendix 14), *Participant Post-Baseline Interview* (Appendix 15), and *SMART App Surveys* (Appendix 16). Table 1 outlines their distribution across the study instruments.

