#### **5.21c Performance Status: ECOG PS**

The Eastern Cooperative Oncology Group (ECOG) Performance Status (PS) assessment is a standard measurement that oncologists often use to assess a patient's current functional level and eligibility for clinical trials. The scale ranges from 0 to 5 and the criteria for each grade is as follows: 0 = Fully active, able to carry on all pre-disease performance without restriction; 1 = Restricted in physically

strenuous activity but ambulatory and able to carry out work of a light or sedentary nature, e.g., light house work, office work; 2 = Ambulatory and capable of all self-care but unable to carry out any work activities; up and about more than 50% of waking hours; 3 = Capable of only limited self-care; confined to bed or chair more than 50% of waking hours; 4 = Completely disabled; cannot carry on any self-care; totally confined to bed or chair; 5 = Dead.

The ECOG PS will allow clinicians and participants to provide a standard evaluation of the participant's performance status over time and with minimal burden. Participants will use the patient self-report version that has been used successfully in a study with cancer patients. We expect that it will take 1-2 minutes to answer the question.

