### **Secondary Endpoints**

- 2) Perceived efficacy
- 3) Additional patient outcomes, including: health-related quality of life, anxiety and depression, symptom burden, and health care utilization
- 4) Agreement between patient and physician estimates of performance status
- 5) Correlation between data collected from the wearable and smartphone accelerometers
- 6) Predictive ability of wearable accelerometer and smartphone data for patient's performance status and clinically significant events

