Patient outcomes: We will collect baseline and 3-month outcome data from patient interviews and clinician surveys. At each time point clinicians and participants will be asked to rate the participant's ECOG performance status and EuroQoL EQ-5D index; patients will also be asked to rate their symptoms using the PRO-CTCAE. We will also collect health care utilization data (e.g. nursing calls, emergency department visits, hospitalizations, and hospice referrals) from the medical chart and healthcare utilization logs provided by patients. For purposes of estimating outcomes parameters, the distributions of these patient outcomes will be summarized using descriptive statistics such as means, standard deviations, and proportions, and, where appropriate, cumulative incidence functions. Additional demographic information that will be summarized include age, marital status, race/ethnicity, education, household structure, income, employment, health literacy and numeracy, and cancer treatment associated burden. We will abstract information from the medical chart; e.g., comorbid health conditions, prior chemotherapy regimens, and time since diagnosis.

Correlative analyses:

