Agreement between patient-oncologist estimates of performance status will be estimated by Cohen's Kappa statistic. We will descriptively summarize correlations between active (e.g. quality of life and symptoms) and passive (e.g. time spent away from home) data collected from the SMART and Beiwe apps and the wearable accelerometer (average daily steps) with clinical outcomes collected at baseline and post-baseline (i.e. performance status, quality of life, and symptoms assessment as obtained from the PRO-CTCAE and CTCAE). In addition to descriptive analyses and estimating correlations between passive smartphone data and clinical outcomes, passive data may contain information that allows for the prediction of future clinically-relevant events, such as visits to the emergency department, urgent clinic encounter, or hospitalization. By testing for changes in activity, mobility, and social patterns over time as measured through smartphone use may be able to identify significant anomalies in patient behavior in the days prior to relapse. In a study in a cohort with schizophrenia, behavioral anomalies detected in the two weeks prior to clinical relapse occurred at a rate 71% higher than anomalies detected on other days. The method is based on a modification of the Hotelling's T test to detect changes in the distribution of previous passively-measured activity. In our proposed study, this method might be used to query patients in real time to detect if an unscheduled clinical event might occur in the near future.

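### SMART's patient–physician ECOG agreement endpoint relies on a clinician survey that the SMART schedule and procedures do not contain

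*Combined protocol and SAP*

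**What the plan says.** All references are to Part 2 (SMART) unless HOPE is named.

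- Section 6.1 lists as secondary endpoint 4: "Agreement between patient and physician estimates of performance status".
- Section 6.3, correlative analyses, names Cohen's kappa as the statistic, in the sentence that opens "Agreement between patient-oncologist estimates of performance status will be estimated by".
- Section 6.3, patient outcomes, names the source: "We will collect baseline and 3-month outcome data from patient interviews and clinician surveys". The sentence after it puts clinicians alongside participants as raters at both times and adds symptom ratings for patients: "ECOG performance status and EuroQoL EQ-5D index; patients will also be asked to rate their symptoms".
- Section 5.21c agrees on who rates performance status, in the sentence that opens "The ECOG PS will allow clinicians and participants to provide a standard evaluation of the".
- Section 6.3 also plans to correlate app and accelerometer data with clinical outcomes, among them "symptoms assessment as obtained from the PRO-CTCAE and CTCAE".

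On the operational side, section 5.4 says that Table 2 sets out the timelines for instruments and interventions. Section 5.5.1 describes how each instrument is administered.

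**The concern.** A kappa for patient–physician agreement needs two ratings of the same patient at about the same time. The analysis sections assume both. The sections that tell a site what to do at Visit 0 and Visit 90 provide only the patient's rating. Analysts cannot make up the missing half afterwards, so the mismatch matters more than an unstated analysis detail would. At stake are endpoint 4, the summary of clinician-rated EQ-5D, and the CTCAE part of the correlations.

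**Working it through.** There is no stated figure to reproduce. The check sets what the analysis needs against what the operational sections provide.

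**Step 1. What the analysis needs.** Clinician ECOG at baseline and 3 months (6.1, 6.3, 5.21c), clinician EQ-5D at the same times (6.3), and CTCAE (6.3).

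**Step 2. The schedule and procedures, which are the main evidence.**
- Table 2 has ten rows: the baseline and post-baseline participant interviews, health/treatment information, health care utilization with call log, debriefing interviews, two rows of app questions, the medical care resource form, passive app data and accelerometer data. None is a clinician survey.
- Section 5.5.1 covers the participant baseline and post-baseline surveys, app surveys, debriefing interviews and two chart abstractions. None has a clinician rating the patient.

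**Step 3. Other places, which carry less weight.**
- The instrument list in 5.21 names two participant interviews and the app surveys.
- Table 1 has columns for those three only and no CTCAE row.
- Among the appendix titles, the only instrument completed with clinicians is a debriefing interview (Appendix 21). Section 5.23 describes its purpose as feedback on the study.
- Section 5.21e covers PRO-CTCAE only.
- The chart items listed in 5.22a and 5.22b do not include performance status or CTCAE.

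**Step 4. Comparison with HOPE (Part 1).** HOPE has each missing piece: a Clinician Survey in its instrument list (5.21), in its Table 1, as a row in Table 3 at Visits 0, 30, 90 and 180, as a procedure in 5.5.1, and as Appendix E. HOPE 5.21e assigns CTCAE to clinicians. The gap is therefore specific to SMART. It recurs in several separate SMART places, so one badly extracted table does not explain it.

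**Step 5. The CTCAE item.** The SMART sentence that uses CTCAE closely matches one in HOPE 6.4 (first phase, correlations with clinical outcomes). It may be carried-over wording and not a planned SMART measurement.

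**Step 6. Size.**
- Patients: 30 (6.2). Time points: 2 (6.3).
- Clinician ECOG ratings: 30 × 2 = 60 at most, fewer if patients die or withdraw before 3 months. The same count applies to clinician EQ-5D.
- Completion time at HOPE's estimate of 5 minutes per clinician survey (HOPE 5.5.1): 60 × 5 = 300 minutes = 5 hours, across at most 2 sites (6.2).

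**The case against.** The best reply is that the rating is planned. Section 6.3 says who rates (clinicians), what (ECOG and EQ-5D), when (baseline and 3 months) and by what means (clinician surveys), and 5.21c names clinicians too. On this view only a form, a table row and a procedure line are missing. That is right as far as it goes, and a reader who inferred that SMART plans no clinician rating would be wrong. But a site coordinator works from the schedule and procedures, and those are the places that are silent.

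Second, several of the lists are weak proof of absence. The instrument list opens with "The following measures will be used in the study interviews and surveys, including the", which is not exhaustive wording. Table 1 is titled for the participant interviews and omits the FACT-G7, although the app administers it (5.21g, 5.52a). The appendix titles omit the Medical Care Resource Form, which is in Table 2 and 5.5.1. This stands, and the point therefore rests on Table 2 and 5.5.1.

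Third, a reader might infer that endpoint 4 could not be reported and that a missed baseline rating is lost for good. The documents do not support that. Section 5.21c describes ECOG as a measure oncologists often use, charts are reviewed for both time points (5.5.1), the abstraction lists use open-ended wording, and the contents of Appendices 17 and 18 cannot be seen. Some ratings could be found in charts. Retrieval is possible but not planned, and a chart rating need not date from the day of the patient's own rating.

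Fourth, section 5.5 lets study activities be adapted without an amendment where there is no added risk. That makes the repair easy; it does not make it happen.

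Finally, materiality is low. The secondary objectives (2.2) do not name agreement, and SMART is descriptive with no formal testing (5.1, 6.3). This stands in full.

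**Conclusion.** The inconsistency is real and worth correcting. Endpoint 4 and its kappa need clinician ECOG ratings that 6.3 promises and that neither Table 2 nor 5.5.1 collects, and 6.3 uses a CTCAE assessment with no collection step anywhere in SMART. Up to 60 clinician ECOG ratings, and as many clinician EQ-5D ratings, are at risk. How many would be missed depends on two things the documents do not settle: whether sites follow the schedule or act on 6.3, and how often charts hold a usable clinician rating.

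The effect is confined to secondary, descriptive results. Feasibility and acceptability, the primary endpoints, do not use clinician ratings and are unaffected.

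**What to change.** Reconcile 5.21c, 6.1 and 6.3 with Table 2 and 5.5.1 in one of two ways.

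(a) **Keep the endpoint.** Add the clinician survey that 6.3 already promises, at Visits 0 and 90, to Table 2, section 5.5.1, the instrument list in 5.21 and the appendices. It needs ECOG performance status; include clinician EQ-5D and CTCAE only if those analyses are kept, and otherwise remove them from 6.3. The cost is one schedule row, one short form, and about 5 clinician-hours of completion time at HOPE's estimate. Staff time comes on top, since HOPE's own procedure involves follow-up of unreturned surveys. Patients already past Visit 0 would have a baseline pair only if a chart rating can be found, so the change is worth most if made early.

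(b) **Drop it.** Delete endpoint 4, the clinician surveys and clinician ratings in 6.3, the clinician wording in 5.21c, and the kappa and CTCAE items in the correlative analyses. The cost is text edits and the loss of one descriptive secondary endpoint.

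Either resolves the conflict. The choice turns on whether the study team still wants patient–physician agreement from the community sites.
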